1.2.2.3 Itraconazole and Hedgehog Pathway Inhibition

Pre-clinical and emerging clinical data suggest that itraconazoleis a potent inhibitor of the Hedgehog pathway. In a drug screen study of ~ 2400 FDA-approved or post-phase I drugusing a cell line containing a stably integrated *GLI1*-luciferase reporter which responds to exogenous stimulation by Sonic hedgehog signaling protein (SHH), itraconazole was identified as a potent inhibitor of the Hh pathway with an IC₅₀ of approximately 800 nM,greater than 10-fold more potent than that of ketoconazole (see figure 3 below) [29].

Figure 3. Itraconazole Potently Inhibits Hedgehog Pathway Relative to Other Azoles

Further experiments in *PTCH*-null and mutant *SMO* cell lines indicate that itraconazole inhibits the Hh pathway via a mechanism distinct from its effects on sterol biosynthesis by acting as an inverse agonist of *SMO*, thereby preventing its accumulation within the primary cilium. In a follow up study using a mouse xenograftmedullablastoma model with constitutively active Hhsignaling, itraconazole inhibited the growth of tumor allografts at steady-state serum concentrations comparable to those of patients treated with 200-300 mg PO BID on a chronic basis for fungal infections (see figure 4 below) [29].

Figure 4.Itraconazole Inhibits In Vivo Growth of a MedulloblastomaXenograft

In a recently presented phase II open label study of 19 patients with basal cell carcinoma, treatment with itraconazole (dosed at either 200 or 400 mg/day) led to a 23% reduction in clinical tumor area and a 65% reduction in Hedgehog activity as assessed by *GL11* mRNA expression [30]. In an intriguing correlative study from the previously described phase II trial of low- and high-dose itraconazole in patients with CRPC, modulation of Hh pathway activity was assessed by serial skin biopsy. Tissue samples were assayed for *GL11* mRNA expression by qRT-PCR, using previously validated methods [25]. In this analysis, 33% of patients treated with itraconazole 200 mg/day and 68% of patients treated with 300 mg PO BID experienced a decrease in*GL11* expression [31]. Interestingly, *GL11*downregulation appeared to be associated with an improvement in PSA progression-free survival, the primary endpoint of the study (see figure 5 below).

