2.2.3 Correlative Objectives

Endocrine Parameters

- To determine the mean percent change from baseline in serum androgen levels, including serum testosterone, DHEA-S, and androstenedione, after 4 and 12 weeks of protocol therapy with itraconazole.
- To determine the mean percent change from baseline in additional serum hormone levels, including adrenocorticotropic hormone (ACTH), aldosterone, deoxycorticosterone (DOC), 11-deoxycortisol, and cortisol after 4 and 12 weeks of protocol therapy with itraconazole.

• To determine if there is a relationship between baseline and/or percent change in serum hormone levels and achieving a decline of $\geq 50\%$ in serum PSA after 12 weeks of protocol therapy.

Hedgehog Pathway:

- To determine the proportion of patients treated with itraconazole who display a downregulation of the Hedgehog pathway, as assessed by measurement of *GL11* mRNA expression by qRT-PCR on serial skin biopsies obtained at baseline and after 4 weeks of protocol therapy. Down-regulation will be defined as a decline of any magnitude in *GL11* mRNA expression after 4 weeks of protocol therapy compared to baseline expression level.
- To determine if there is a relationship between down-regulation of the Hedgehog pathway and PSA modulation, including proportion of patients achieving a decline of \geq 50% in serum PSA as well as time to PSA progression.
- To evaluate archived primary prostate cancer tissue (biopsy or prostatectomy specimen) for baseline Hedgehog pathway status, using both qRT-PCR-based mRNA expression analysis and protein-based immunohistochemical (IHC) analysis of key Hh pathway components (*GLI1*, *PCTH1*, *SMO*) and Sonic hedgehog ligand.
- To determine if there is a relationship between mRNA and ICH expression of components in the Hedgehog pathway in primary prostate cancer tissue and PSA modulation on itraconazole therapy, including the proportion of patients achieving a decline of \geq 50% in serum PSA as well as time to PSA progression.

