9.2 Hedgehog Pathway Assessment BymRNA Expression Analysis

Because Hedgehog signaling is present in skin and hair follicles, *GL11* mRNA expression (a marker of Hedgehog pathway activation) will be analyzed using 3-millimeter skin punchbiopsies from hair-containing non-scalp skin (e.g. upper back or arms) obtained at baseline and after 4 weeks on study, using previously described and validated methodology [25]. The skin sample should be placed immediately into a 5 mL Tissue Protect Tube containing RNAlater solution, and care must be taken to ensure that the skin sample is fully submerged in RNAlater. Samples should then be frozen at -20 degrees Celsius or colder until the time of RNA extraction. Additionally, mRNA expression analysis of archived, formalin-fixed paraffin embedded primary prostate cancer tissue will be performed when tissue is available. Please see Appendix 3 for details regarding the skin biopsy procedure as well as specimen handling/shipping instructions.

*GLI1*mRNA expression levels in tissue samples will be analyzed using the RT² Profiler Custom PCR Array protocol (SABiosciences, Qiagen). RNA will be extracted from tissue samples using RNeasy Fibrous Tissue kit (Qiagen). The RT² PCR Array First Strand kit (SuperArray Bioscience), will be used to synthesize cDNA. Quantitative PCR will be performed using RT² Real-Time SYBR Green PCR Master Mix (SABiosciences, Qiagen), in an ICycler PCR System (Bio-Rad Laboratories), according to the manufacturer's protocol. The housekeeper gene *GAPDH* will be used, as the expression level of this gene has been previously shown to not change with itraconazole therapy using a housekeeper array (Cat#: PHAS-000, SABiosciences, Qiagen). Cycling threshold (C_t) values for *GLI1*and *GAPDH* from each experiment will be analyzed using the SABiosciences software and fold change of *GLI1*expression, normalized to *GAPDH*, will be derived for each sample.

Patients will be dichotomized for the purposes of statistical analysis. The full statistical analytic plan for *GLI1* expression datais described in Section 10.

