10.8.3 Analytic Plan for the Correlative Objectives

Endocrine Parameters

Serum hormone levels, including testosterone, androstenedione, DHEA-S, cortisol, aldosterone, 11-deoxycortisol, ACTH, and deoxycorticosterone, will be measured at baseline, at week 4, week 12, and at the time of PSA or clinical progression. To summarize the outcome, descriptive statistics including the mean percent change from baseline in serum hormone levels at 4 and 12 weeks will be presented with a standard deviation and Pearson"s correlation will be used to estimate the relationship between the baseline hormone level and percent change in hormone level after 4 and 12 weeks of treatment. Analysis of variance (ANOVA) methods for mixed models allowing for variable number of follow-up measurements with linear contrasts will be used to evaluate the change in serum hormone levels after 4 and 12 weeks of protocol therapy. It is hypothesized that approximately 15% of patients treated with protocol therapy will achieve a PSA decline \geq 50%. Depending upon the observed frequency, the ANOVA model will include a factor to test for the effect of PSA decline on change in serum hormone levels. Otherwise, analyses will compare the baseline and percent change in serum hormone levels at 4 and 12 weeks between patients achieving a PSA decline $\geq 50\%$ or not using a two group t statistic. For these exploratory analyses, graphic presentations will also be used to explore the overall pattern of change in serum hormone levels between those with and without a PSA decline.

Hedgehog Pathway

The quantitative expression of *GLI1*, a downstream product of the Hedgehog signal transduction pathway, will be measured by quantitative RT-PCR from serial skin biopsies obtained at baseline and after 4 weeks of therapy. The fold change in expression level after 4 weeks of protocol therapy will be calculated for each patient. Descriptive statistics will be used to summarize the proportion of patients with down-regulation of *GLI1* expression after 4 weeks of treatment with itraconazole. Down-regulation will be defined as any magnitude of decrease in *GLI1* mRNA expression after 4 weeks of protocol therapy compared to baseline expression level. The patient

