cohort will be dichotomized by whether there is up- or down-regulation of *GL11* expression. Fisher's exact test will be used to test for an association between down-regulation of *GL11* expression and PSA decline 50% on protocol therapy. The probability distributions for each *GL11* expressionsubset (as defined above) of the time to PSA progression will be estimated using the Kaplan-Meier product limit method. The results will be summarized by the estimated median with 95% confidence intervals. An exploratory analysis using the log-rank test will be used to test for differences in the distributions between patients with down-regulation of *GL11* expression vs. those without *GL11* down-regulation on therapy.

The quantitative expression of *GLI1* will also be measured by quantitative RT-PCR from archived primary prostate cancer tissue. The patient cohort will be dichotomized by expression level of *GLI1* (above vs. below the median). Fisher's exact test will be used to test for an association between *GLI1* expression in primary prostate cancer tissue and PSA decline $\geq 50\%$ on itraconazole therapy. The probability distributions for each *GLI1* expression subset of the time to PSA progression will be estimated using the Kaplan-Meier product limit method. The results will be summarized by the estimated median with 95% confidence intervals. An exploratory analysis using the log-rank test will be performed to test for differences in the distributions between patients with *GLI1* expression above vs. below the median from primary prostate cancer tissue specimens.

Immunohistochemical analysis of primary prostate cancer tissue for protein expression of *PCTH1*, *GL11*, *SMO*, as well as Sonic hedgehog ligand will be carried out for patients with evaluable tissue. It is estimated that approximately 50% of patients will have tissue available for analysis. Immunohistochemical expression will be graded as 0, 1+, 2+, and 3+ staining intensity by independent, blinded pathologic assessment. For each protein, the patient cohort will be dichotomized based on intensity of IHC staining (0 and 1+ vs. 2+-3+). Fisher''s exact test will be used to test for an association between IHC expression and PSA decline > 50% on protocol therapy. The probability distibutions for each expression subset of the time to PSA progression will be estimated using the Kaplan-Meier product limit method. The results will be summarized by the estimated median with 95% confidence intervals.

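### GLI1 mRNA is measured quantitatively but related to PSA outcomes only as two groups; a few continuous exploratory analyses beside the planned tests would be a cheap improvement (minor)

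*Combined protocol and SAP*

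**What the plan says.** Sections 9.2 and 10.8.3 describe GLI1 measurement by quantitative RT-PCR, normalised to a housekeeping gene. For skin, 10.8.3 states: "The fold change in expression level after 4 weeks of protocol therapy will be calculated for each patient". Section 9.2 then gives the general rule for the mRNA data: "Patients will be dichotomized for the purposes of statistical analysis".

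For skin, 10.8.3 says the "cohort will be dichotomized by whether there is up- or down-regulation of" GLI1. The cut comes from Section 2.2.3: "Down-regulation will be defined as a decline of any magnitude in" GLI1 expression. For archived tissue, 10.8.3 says: "The patient cohort will be dichotomized by expression level of" GLI1, above versus below the median. That median split also stands in the correlative endpoints (3.2.3 and 10.7.3), although the objective in 2.2.3 names no cut and asks about "a relationship between mRNA and ICH expression of components in the Hedgehog pathway in primary prostate cancer tissue and PSA modulation".

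Each split is related to a PSA decline of at least 50% by Fisher's exact test, and to time to PSA progression by Kaplan-Meier medians and a log-rank test. For tissue the latter reads: "An exploratory analysis using the log-rank test will be performed to test for differences in the distributions between patients with" high versus low expression. No section plans a rank test, correlation or regression on the GLI1 values themselves. In the same section, serum hormone levels are compared between PSA responders and non-responders as continuous values. No multiplicity adjustment is made for correlative objectives.

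**The concern.** Relating the Hedgehog pathway to PSA modulation is a stated correlative objective, and Section 5.3.3.2 presents the tissue work as a possible first step toward a predictive biomarker. If the relation is graded, reducing a measured value to two groups discards information. The response analysis is already short of information, because few responders are expected among those with tissue.

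Two things are at stake. A non-significant Fisher result in tissue could be read as evidence against the pathway when the test had little or no chance of being significant. And if nothing continuous is specified now, any such analysis done later will be post hoc.

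**Working it through.** **Plan's own figures.** The documents give no power figure for the GLI1 analyses. The primary design in 10.2 (22 then 40 patients, continue if more than 2 respond, reject at 8 or more) reproduces by exact binomial calculation: early stopping under 10% is P(X≤2 | 22, 0.10) = 0.620 (stated 0.62), type I error is 0.040 (limit 0.05), and power at 25% is 0.803 (stated 0.80). Nothing below affects it.

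**Inputs.**
- 40 evaluable patients (10.2).
- About 50% with archived tissue (9.3, and the immunohistochemistry paragraph of 10.8.3). Applied to tissue mRNA as an assumption, this gives 20 samples, split 10/10 at the median.
- Response rate 15% (10.8.3) or 25% (alternative in 10.2): 3 or 5 expected responders of 20.
- Skin: 68% down-regulated at 300 mg BID in the earlier castrate-resistant trial (1.2.2.3). Biopsy is optional (6.3.6), so n=40 is an upper limit.
- Two-sided 0.05 is assumed; the documents state no threshold for these tests.

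**Smallest attainable p in tissue.** With k responders all in one half of a 10/10 split, the two-sided Fisher p is 2·C(10,k)/C(20,k):
- k=3: 2·120/1140 = 0.21
- k=4: 2·210/4845 = 0.087
- k=5: 2·252/15504 = 0.033

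So at least 5 responders are needed. P(X≤4 | 20, p) is 0.83 at p=0.15 and 0.41 at p=0.25. An exact Wilcoxon test on the same 20 values has a minimum p of 2/C(20,3) = 0.0018 with 3 responders.

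**Skin.** With a 27/13 split and all 6 expected responders (15% of 40) in the down-regulated group, Fisher p = 0.15. In that arrangement 8 responders give p = 0.037.

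**Power for PSA response** (simulation, at least 4,000 runs per cell). In the graded model, GLI1 and PSA change are bivariate normal with assumed correlation 0.5, and responders are the lowest 25% or 15% of PSA change. In the step model, response depends only on the side of the planned cut.

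| Scenario | Fisher on split | Wilcoxon on values |
|---|---|---|
| Tissue n=20, graded, 25% | 0.10 | 0.33 |
| Tissue n=20, graded, 15% | 0.03 | 0.22 |
| Skin n=40, graded, 25% | 0.27 | 0.63 |
| Skin n=40, graded, 15% | 0.09 | 0.52 |
| Skin n=20, graded, 25% | 0.05 | 0.32 |
| Skin n=40, step 37% vs 0% | 0.76 | 0.53 |
| Skin n=40, step 22% vs 0% | 0.20 | 0.24 |
| Tissue n=20, step 50% vs 0% | 0.62 | 0.63 |
| Tissue n=20, step 30% vs 0% | 0.15 | 0.27 |

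With no association, tissue Fisher rejects in about 1% of runs and Wilcoxon in about 4%, so part of the gap is Fisher's conservatism.

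**Power for time to PSA progression** (exponential times; censoring mean three times the baseline mean; higher GLI1 carrying higher hazard).

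| Scenario | Log-rank on split | Cox on values |
|---|---|---|
| Tissue n=20, hazard ratio 2 per SD | 0.41 | 0.60 |
| Skin n=40, hazard ratio 2 per SD | 0.75 | 0.91 |
| Tissue n=20, step hazard ratio 3 | 0.55 | 0.36 |
| Skin n=40, step hazard ratio 3 | 0.82 | 0.49 |

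Both tests here share one time origin, so the skin rows are only indicative for a model that starts at the week-4 biopsy.

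**The case against.** The strongest defence is that the planned tests answer the stated questions. In skin, any decline is the protocol's definition of down-regulation. It also matches the form of the earlier evidence, in which GLI1 down-regulation "appeared to be associated with an improvement in PSA progression-free survival" (1.2.2.3). A reader might infer from the objective in 2.2.3 that the tissue median split is merely an analyst's choice in 10.8.3. The documents do not support that: 3.2.3 and 10.7.3 write it into the endpoint. This part of the defence stands, and it is why the planned tests should be kept.

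Second, a gain is not guaranteed. If the effect is a step, the planned log-rank test is clearly stronger, and Fisher can be too. The documents do not say which shape holds. This also stands.

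Third, a reader might credit the whole gain from a Spearman correlation with percent PSA change to keeping GLI1 continuous. The figures do not support that. In tissue (correlation 0.5, 25% response), power is 0.10 for Fisher, 0.38 with GLI1 still split but PSA change continuous, and 0.58 for Spearman. So 0.28 of the 0.48 gain arises before GLI1 is touched. Percent PSA change is also not among the Hedgehog endpoints.

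Last, these are exploratory analyses. Any biomarker would need prospective validation (5.3.3.2), and continuous tissue power for response is still only about a third at best in these graded scenarios. That limits the importance of the point. It does not explain why values already collected should have no pre-specified analysis.

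**Conclusion.** The point holds as a minor, cheap improvement. It is not an error in the plan, and it does not touch the primary endpoint, sample size or decision rule.

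The firmest part is the Fisher limit in tissue: with a 10/10 split and four or fewer responders, p<0.05 is out of reach even with perfect separation. That is more likely than not at a 15% response rate (0.83) and quite possible at 25% (0.41). It depends only on the assumed 20 samples, the response rate and the assumed threshold.

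The power comparison is conditional. It favours the continuous analysis if the relation is graded and monotone, and rests on assumed effect sizes, normality and biopsy uptake. It would be wrong to conclude that the planned tests should be replaced, or that continuous analysis is always stronger. The main benefit is an estimate with an interval, specified in advance.

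**What to change.** Keep every planned dichotomised analysis. Add to 10.8.3, for log2 GLI1 fold change (skin) and log2 normalised GLI1 expression (tissue), the following analyses, labelled exploratory and reported as estimates with 95% confidence intervals:

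1. An exact Wilcoxon comparison of GLI1 between PSA responders and non-responders, with a Hodges-Lehmann shift and interval, using the response definition and failure rules of 10.8.1.
2. Cox regression for time to PSA progression, giving a hazard ratio per log2 unit. Time runs from the start of therapy for tissue and from the week-4 biopsy for skin. State that the skin origin differs from that of the planned log-rank test, which follows 10.8.2 in counting from the start of therapy.

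A Spearman correlation with percent PSA change at week 12 is optional. If added, label it as an outcome outside the endpoint list and fix one rule for men without a week-12 PSA.

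The cost is SAP wording only: no new samples, visits or assays. The downside is two further unadjusted exploratory analyses for each of two GLI1 measures (three with the optional correlation), with wide intervals at n=20.

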11.0 Reporting and Documentation of Adverse Events

11.1 Definitions of Adverse Events (21 CFR 312.32(a))

Adverse Event

Adverse event means any untoward medical occurrence associated with the use of a drug in humans, whether or not considered drug related.

An *adverse event* (also referred to as an adverse experience) can be any unfavorable and unintended sign (e.g., an abnormal laboratory finding), symptom, or disease temporally associated with the use of a drug, without any judgment about causality. An adverse event can arise from any use of the drug (e.g., off-label use, use in combination with another drug) and from any route of administration, formulation, or dose, including an overdose.

Adverse reaction

An adverse reaction means any adverse event caused by a drug. Adverse reactions are a subset of all suspected adverse reactions for which there is reason to conclude that the drug caused the event.

Suspected adverse reaction

Suspected adverse reaction means any adverse event for which there is a reasonable possibility that the drug caused the adverse event. For the purposes of IND safety reporting, "reasonable possibility" means there is evidence to suggest a causal relationship between the drug and the adverse event. A suspected adverse reaction implies a lesser degree of certainty about causality than adverse reaction, which means any adverse event caused by a drug.

Unexpected

An adverse event or suspected adverse reaction is considered "unexpected" if it is not listed in the investigator brochure or package insert(s) or, is not listed at the specificity or severity that has been observed; or, if an investigator brochure is not required or available, is not consistent with the risk information described in the general investigational plan or elsewhere in the current application.

"Unexpected," as used in this definition, also refers to adverse events or suspected adverse reactions that are mentioned in the investigator brochure as occurring with a class of drugs or as anticipated from the pharmacological properties of the drug, but are not specifically mentioned as occurring with the particular drug under investigation.

Adverse events that would be anticipated to occur as part of the disease process are considered *unexpected* for the purposes of reporting because they would not be listed in the investigator brochure. For example, a certain number of non-acute deaths in a cancer trial would be anticipated as an outcome of the underlying disease, but such deaths would generally not be listed as a suspected adverse reaction in the investigator brochure.

Some adverse events are listed in the investigator brochure as occurring with the same class of drugs, or as anticipated from the pharmacological properties of the drug, even though they have not been observed with the drug under investigation. Such events would be considered *unexpected* until they have been observed with the drug under investigation. For example, although angioedema is anticipated to occur in some patients exposed to drugs in the ACE inhibitor class and angioedema would be described in the investigator brochure as a class effect,

the first case of angioedema observed with the drug under investigation should be considered *unexpected* for reporting purposes.

Serious

An adverse event or suspected adverse reaction is considered "serious" if, in the view of either the investigator or sponsor, it results in any of the following outcomes:

- Death
- a life-threatening adverse event
- inpatient hospitalization or prolongation of existing hospitalization
- a persistent or significant incapacity or substantial disruption of the ability to conduct normal life function
- a congenital anomaly/birth defect

Important medical events that may not result in death, be life-threatening, or require hospitalization may be considered serious when, based upon appropriate medical judgment, they may jeopardize the patient or subject and may require medical or surgical intervention to prevent one of the outcomes listed in this definition. Examples of such medical events include allergic bronchospasm requiring intensive treatment in an emergency room or at home, blood dyscrasias or convulsions that do not result in inpatient hospitalization, or the development of drug dependency or drug abuse.

Life-threatening

An adverse event or suspected adverse reaction is considered "life-threatening" if, in the view of either the investigator or sponsor, its occurrence places the patient or subject at immediate risk of death. It does not include an adverse event or suspected adverse reaction that, had it occurred in a more severe form, might have caused death.

